6.4. Pooling of Small Sites

Pooling of sites will be performed only once prior to any efficacy statistical analysis.

Any investigator center having less than 2 subjects in any given treatment group or efficacy outcome category within each age group strata will be defined as a 'small' center. The pooling of small centers will be based on the total number of subjects randomized at each center. Small centers will be pooled to large centers within the same country. When there are only small centers within a given country, small centers will be pooled to large centers within the same region.

Small centers will be pooled with other similar small centers using the following process:

Part A: Pool centers based on frequency in binary efficacy endpoints in the 12-16 year old stratum and the ≤ 55 kg stratum.

1. For the completer subjects population, create a center by CAR 9-52 frequency table (say Table 1).
2. Identify small centers from Table 1 (small center defined as a center with a 0 count in any column of Table 1).
3. Identify the country for each small center.
4. Within each country, independently order the small centers and the non-small centers (those with non-zero cells) based on the total number of subjects in the center.
5. Within each country, pool the smallest small (zero-cell) center to the largest non-small (non-zero cell). Then pool the next smallest small center to the next largest non-small center, and so on, until all small centers have been pooled with a non-small center. At this point the center by CAR 9-52 frequency table should not have any cell with zero frequency.
6. Renumber the pooled centers after the last two centers are pooled.
7. Repeat Steps 1 to 6 for each of the other efficacy endpoints to ensure there are no zero frequency cells in the frequency table of pooled center by any binary endpoint.

Part B: Pool centers based on frequency in each treatment group. Repeat 'Part A' by replacing the binary endpoint with treatment group data.

After applying 'Part A' and 'Part B', check the convergence of the CAR 9-52 model that includes treatment groups and centers (pooled centers) on the Completers population:

- If model converges, check the convergence of all other logistic models specified in this SAP.

- If model does not converge (unlikely) apply ‘Part C’ described below.

Part C:

Repeat ‘Part A’ and ‘Part B’ with small center defined as a center with a count of 1 in any column of Table 1.

Notes:

- a. If two centers have same frequency, select the one with the smallest center number.
- b. If for a given country, there is only one center, replace country by region in Steps 3 to 6 above (only for the given country, for other countries do as specified above).

The final pooled centers will be used in the analysis for the rest of the efficacy endpoints.

6.5. Covariates

Age Strata, body weight strata, and center will be included in statistical models as fixed effects. The additional effects of treatment by center interaction, treatment by age, and treatment by body weight may be included in exploratory models.

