9.1. Sample Size Determination

Although analysis for the primary efficacy endpoint will be model based, the sample size calculation is based on a two-sided Chi-Square test with a 0.05 significance level and a 1:1:1 randomization ratio of varenicline 1 mg BID to varenicline 0.5 mg BID to placebo. The study is powered at 80% or greater to detect varenicline (1 mg BID or 0.5 mg BID dose) vs. placebo differences in the CQR from Weeks 9 through 12. The sample size is based on CQR of 9% and 24% for placebo and varenicline respectively, or an odds ratio of 3.2.

A sample size of 300 subjects randomized to varenicline or placebo in a 1:1:1 (100 to varenicline 1 mg BID, 100 to varenicline 0.5 mg BID, 100 to placebo) will provide approximately 80% power to detect a difference in the primary endpoint between varenicline and placebo groups, assuming a true Week 9-12 CQR of 9% and 24% for placebo and varenicline respectively.

Enrollment will be stratified by age group (12-16 vs. 17-19) and sufficient subjects will be enrolled in the 12-16 year old age group to detect a difference in the primary endpoint between varenicline and placebo groups, assuming a true Week 9-12 CQR of 9% and 29% for placebo and varenicline respectively.

In order to ensure sufficient subjects are enrolled in the 12-16 year old stratum, the 17-19 year old stratum will be capped at a maximum of 90 subjects, leaving at least 210 subjects (approximately 70 subjects per treatment group) in the 12-16 year old stratum.

Efficacy Analysis

The primary efficacy inference for the study is a comparison of varenicline to placebo for the CQR for Weeks 9 through 12. This measure will be obtained through reports of cigarette or other nicotine use since the last study visit confirmed by urine cotinine. An exploratory subgroup analysis for each dosing group by weight stratum for the primary endpoint will be provided.

All efficacy analyses will be performed overall as well as on the subgroup of patients who are 12-16 years of age.

Secondary efficacy endpoints are listed in Section [2.2](#).

These efficacy endpoints will be based on subject self-report, with abstinence confirmed by cotinine.

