8.1.1.2. Efficacy Analysis

Logistic regression models will be used in the analyses of primary endpoint, as well as several secondary endpoints. The model will include strata, and pooled center as independent variables. Treatment by center, treatment by age stratum, and treatment by body weight stratum interaction will be investigated. If interactions are significant, then exploratory analyses will be undertaken to explain the nature and source of the interaction. However, the reported p-values will be based on the main effects model.

Additional analyses may be performed adjusting for baseline covariates as additive terms to the primary model, if necessary. Results from any additional analyses will not be used as a substitute for the planned analyses, but may be used as supplemental information for the study report.

In addition, a sensitivity analysis excluding 16 subjects from investigative site PPD will be performed on the primary endpoint – Continuous Abstinence Rate from Week 9 through 12 – using the primary analysis model.

This sensitivity analysis will be performed for the following groups:

- Overall study.
- 12-16 year old age stratum.

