As a sensitivity analysis of the primary endpoint, multiple imputation methods will be used to evaluate the impact of missing data. Subjects who discontinue the study due to insufficient clinical response, adverse event, or death will be imputed based upon the observed placebo distribution, regardless of randomized treatment assignment. Imputation will be based on age stratum, body weight stratum, pooled study center, and baseline number of cigarettes smoked. Subjects who discontinue the study for other reasons, or who complete the study but have a missing Week 9-12 CAR, will be imputed based on observed subjects in the same treatment group. Imputation will be based on treatment, age stratum, body weight stratum, pooled study center, and baseline number of cigarettes smoked.

A final sensitivity analysis will be performed based on discontinuation from treatment, regardless of study completion status.

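### The Week 9–12 abstinence model leaves out baseline cigarettes per day; pre-specifying that one term is a cheap, small improvement, not the repair of an error

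*SAP*

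**What the plan says.** Protocol 9.1.1 puts strata, treatment and centre in the primary logistic model. SAP 6.5 lists the covariates: "Age Strata, body weight strata, and center will be included in statistical models as fixed effects". SAP 8.1.1.2 repeats the list for the logistic models but drops treatment: "The model will include strata, and pooled center as independent variables".

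Further adjustment is optional: "Additional analyses may be performed adjusting for baseline covariates as additive terms to the primary model, if necessary". No covariate is named there, and the same paragraph limits such results to a supplementary role.

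Baseline smoking intensity is used elsewhere in the SAP. Both arms of the multiple-imputation sensitivity analysis of the primary endpoint use it; for discontinuations not due to insufficient response, adverse event or death, the rule is: "Imputation will be based on treatment, age stratum, body weight stratum, pooled study center, and baseline number of cigarettes smoked". It is also a covariate in the cigarette-reduction model (SAP 8.2.4.2).

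The measures are available in time. FTND and a tobacco history are taken at screening (Protocol 6.1). The Nicotine Use Inventory (NUI) is completed at the baseline visit and listed there ahead of randomisation (Protocol 6.2.1). Randomisation is not stratified by smoking severity in either document (Protocol 5.1; SAP 2.1).

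**The concern.** Two things are at stake.

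- **Efficiency.** If heavier smokers are less likely to quit, conditioning on a baseline measure of smoking makes the dose-versus-placebo comparison somewhat more powerful. It also corrects the estimate for whatever imbalance in that measure arose by chance.
- **Pre-specification.** Protocol 9.1 and SAP 8.2.1 tabulate smoking history and dependence by arm, but neither says what follows if the arms differ. With the covariates unnamed and the trigger left open, the decision to adjust, and for what, could be taken after the baseline table and the outcomes are known.

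The plan also treats the variable unevenly: it is thought relevant enough to impute Week 9–12 abstinence, yet is absent from the model that analyses it.

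**Working it through.** **1. The plan's own power.** Protocol 9.1 says that the "sample size calculation is based on a two-sided Chi-Square test with a 0.05 significance level and a 1:1:1 randomization ratio" and "The sample size is based on CQR of 9% and 24% for placebo and varenicline respectively, or an odds ratio of 3.2", with 100 subjects per arm.

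- Odds ratio: (0.24/0.76)/(0.09/0.91) = 3.19, matching 3.2; log OR = 1.16.
- Pooled standard error under no difference: √(2 × 0.165 × 0.835/100) = 0.0525.
- Standard error under the alternative: √((0.09 × 0.91 + 0.24 × 0.76)/100) = 0.0514.
- Power: Φ((0.15 − 1.96 × 0.0525)/0.0514) = Φ(0.916) = 82.0%.

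This agrees with "The study is powered at 80% or greater to detect varenicline". No covariate is involved, so the claim does not depend on adjustment.

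**2. Gain in power from adjustment.** The documents do not say how strongly baseline smoking predicts abstinence, so a range is assumed: an odds ratio of abstinence per standard deviation (SD) of 0.8 to 0.5. All runs simulate three arms of 100 at 9%/24%/24% and test 1 mg BID against placebo.

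| OR per SD | A: one covariate, no strata or centre | B: two covariates (correlation 0.5), strata, 10 centres | C: two covariates (correlation 0.6), strata, 8 centres (gain only) |
|---|---|---|---|
| 0.8 | 82.5 → 82.9% | 83.0 → 83.4% | +0.2 |
| 0.7 | 82.3 → 83.4% | 83.2 → 84.0% | +0.3 |
| 0.6 | 82.9 → 84.0% | 82.5 → 83.7% | +1.0 |
| 0.5 | 82.5 → 84.7% | 82.1 → 84.4% | +1.2 |

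A used 6,000 trials per row (Monte Carlo SE about 0.5 point). B used 3,000 (about 0.7 point). C used 3,000 (paired SE of the gain 0.25–0.43 point), with the odds ratio per SD of an underlying severity that both covariates measure imperfectly. The numbers of centres and the correlations are assumptions.

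An independent one-covariate run gave gains of 0.4 point at 1.25 per SD (the inverse of 0.8), 1.2 at 1.5 and 2.5 at 2.0 (the inverse of 0.5). With an uninformative covariate (OR 1.0), B moved from 83.9% to 83.7%, which is no loss beyond simulation error. Type I error in B with both covariates was 4.7% and 5.4% at ORs of 1.0 and 0.5. No run has exactly the model proposed below, with one covariate plus strata and centres; A and B bracket it.

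**3. Chance imbalance.** The between-arm difference in a standardised covariate has standard error √(2/100) = 0.141 SD. An imbalance of that size shifts the unadjusted log OR by 0.141 × |ln(OR per SD)|.

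- OR 0.8: 0.141 × 0.223 = 0.03, a factor of 1.03.
- OR 0.5: 0.141 × 0.693 = 0.098, a factor of 1.10.

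The standard error of the log OR is √(1/(100 × 0.09 × 0.91) + 1/(100 × 0.24 × 0.76)) = 0.42. The largest of these shifts is therefore 0.098/0.42 = 0.23 of a standard error.

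**4. Information available.** Expected abstainers: 9 + 24 + 24 = 57. That can carry one more term in the overall model. The weight-by-age subgroups have far fewer.

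**The case against.** The strongest reply is that this is a preference. The gain is small, rests on an assumed prognostic strength, and at the weak end lies within simulation error. Randomisation protects the test, and the reported standard error already allows for chance imbalance. Comparability tables and supplementary adjusted analyses are already in the plan. All of this stands, and it limits the point to an improvement.

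The reply also bears on which covariate to add. FTND item 4 is cigarettes per day (Protocol Appendix 2), and entry requires a score of 4 or more (Protocol 4.1), so FTND overlaps with the other measure and has a restricted range. A reader might infer that adding FTND would bring the analysis into line with the imputation. It would not: FTND is not in the imputation model, whereas baseline cigarettes is.

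A missing covariate matters too. SAP 5.1 analyses everyone randomised and SAP 5.5 keeps eligibility violators, while ordinary logistic regression drops a subject with a missing covariate. Any added term therefore needs a missing-value rule.

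What the reply does not answer is pre-specification: permission to adjust for unnamed covariates is not a plan to do so.

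**Conclusion.** The omission is real and worth correcting as a matter of efficiency and pre-specification. Over assumed odds ratios of 0.8 to 0.5 per SD, the gain is about 0 to 2 points of power, and protection against a shift of about 3–10% in the odds ratio at a one-standard-error imbalance. Stronger prognosis would give more (about 4 points at 2.5 per SD), but nothing in the documents supports that value.

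Three stronger readings are not supported.

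- A reader might infer that the trial is underpowered without the term. The stated power is reached without it.
- A reader might infer that chance imbalance biases the test or inflates type I error. It affects the estimate in a given trial, not the validity of the randomised comparison.
- A reader might infer from SAP 8.1.1.2 that no treatment effect is fitted. SAP 4.1 and 8.2.3 make the comparison with placebo plain, so the missing word is a drafting slip.

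**What to change.** Before unblinding, amend SAP 6.5 and 8.1.1.2 as follows.

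- **Week 9–12 model**, overall study and 12–16 stratum: treatment + age stratum (overall only) + weight stratum + pooled centre + baseline cigarettes per day, linear. Use the baseline-visit NUI variable of SAP 8.2.4.2.
- **Missing baseline value:** fill by a simple treatment-blind rule, such as the overall mean, so that no randomised subject is lost. State that the baseline-visit value applies to subjects never dosed, since SAP 6.3 defines baseline by the first dose.
- **Sensitivity analysis:** the present strata-and-centre model.
- **FTND:** in a named supportive model.
- **Scope:** leave the sparse weight-by-age subgroup models unchanged. Because SAP 8.2.4 refers back to 8.1.1.2 for the secondary abstinence endpoints, say explicitly that the new term is for Week 9–12.
- **Drafting:** restore treatment to the model sentence in 8.1.1.2.

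The cost is a few SAP sentences, one model term, and a recorded departure from Protocol 9.1.1, as Protocol section 9 requires. The downside is a change of target: the odds ratio becomes conditional on baseline smoking. In simulation the design value of 3.19 becomes 3.22 at an odds ratio of 1.25 per SD and 3.44 at 2.0, so the report should say which odds ratio is shown.

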7. HANDLING OF MISSING VALUES

Subjects who discontinue the study will be considered smokers for the remainder of the study regardless of their last smoking status evaluation. This implies that subjects who discontinue will continue to be represented in the denominator but not in the numerator regardless of smoking status at the time of discontinuation. This can be considered a worst case carried forward analysis and represents a conservative approach to imputation of missing data.

For the HADS-A and HADS-D, if more than one question within a domain (anxiety or depression) is missing, the score will be set to missing. If only one question is missing, the missing response will be imputed with the domain-specific mean based on the remaining questions.

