2.1. Study Design

This will be a randomized, double-blind, placebo-controlled, multicenter study to compare two doses of varenicline 1 mg BID and 0.5 mg BID with placebo for smoking cessation in adolescent smokers aged 12-19 years who are motivated to quit. Since varenicline exposure is related to body weight, subjects with a body weight ≤ 55 kg will have their varenicline dose reduced by half (those randomized to 1 mg BID will receive 0.5 mg BID and those randomized to 0.5 mg BID will receive 0.5 mg QD).

[figure not shown]
Randomization will be stratified by age group (12-16 vs 17-19) and body weight. In order to ensure a sufficient number of subjects in the 12-16 year old stratum, the 17-19 year old stratum will be capped at a maximum of 90 subjects.

Those subjects deemed eligible will be randomized and enter the 12-week placebo-controlled treatment period with weekly clinic visits for efficacy and safety assessments and smoking cessation counseling. Varenicline or placebo dosing will begin with two weeks of titration. (Figure 1). All subjects will set a target quit date (TQD) to coincide with the Week 1 visit. The Week 1 visit occurs at the end of the first week of the treatment phase. The primary efficacy endpoint will be complete abstinence from smoking, biochemically verified, during the last 4 weeks of the 12 week dosing period.

Follow-up period: Subjects will be followed to obtain smoking status for 9 months after the end of the 12-week treatment period. Clinic visits will occur at Weeks 13-16 (inclusive), 20, 28, 36, 44, and 52. Telephone visits are planned for Weeks 24, 32, 40, and 48.

The clinical trial is illustrated in [Figure 1](#).

Figure 1. Study A3051073 Trial Diagram

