5. ANALYSIS SETS

In each of the following efficacy populations, subjects who discontinue the study are assumed to be smokers from the time point of discontinuation through the end of the study.

In computing responder rates, subjects who discontinue the study will be included in the denominator but not in the numerator, regardless of their last smoking status evaluation.

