5.1. Full Analysis Set

The primary efficacy analysis population will be the Full Analysis Set, defined as all subjects who were randomized.

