8.1.1. Analyses for Categorical Data

8.1.1.1. Descriptive Statistics

Categorical data will be summarized by presenting the counts and percentages with the denominator being the number of subjects in the analysis set in the particular treatment group with non-missing data.

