8.2.3. Primary Efficacy Analysis

The primary efficacy analysis will be analysis of *the 4-week continuous abstinence rate (CAR) from Week 9 through Week 12 of treatment for each varenicline treatment group compared with placebo*.

The 4-week CAR will be summarized by treatment group using descriptive statistics and bar charts.

This will be summarized for the following groups:

- Overall study.
- 12-16 year old age stratum.
- 12-16 year old age stratum, ≤ 55 kg weight stratum.
- 12-16 year old age stratum, > 55 kg weight stratum.
- 17-19 year old age stratum.

The 4-week CAR will be analyzed using a logistic regression model as described in [Section 8.1.1.2](#). Odds ratios and 95% confidence intervals will be shown in plots.

These will be analysed for the following groups:

- Overall study.
- 12-16 year old age stratum (without age strata covariate).
- 12-16 year old age stratum, ≤ 55 kg weight stratum (without age strata or body weight strata covariates).
- 12-16 year old age stratum, > 55 kg weight stratum (without age strata or body weight strata covariates).

While the analysis will be performed for sets listed above, the primary analysis of the primary efficacy endpoint is the overall study.

Statistical hypotheses for the primary endpoint will be tested in an ordered fashion to preserve overall Type I Error. The 1 mg BID group will be tested against placebo, and if a statistically significant difference is observed, the 0.5 mg BID group will be tested against placebo. A p-value of 0.05 will be considered statistically significant in both tests. Both tests will be presented regardless of the p-value obtained.

A sensitivity analysis excluding site **PPD** will be performed based on the primary analysis of the primary endpoint. This site was terminated based on concerns regarding GCP non-compliance.

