8.2.5. Additional Efficacy Analysis

Subjects who reported using any non-study smoking cessation aids during the non-treatment follow-up period will be displayed in a table described in [Section 8.1.1.1](#). Additionally, this subset of concomitant medication use will be listed in a separate listing.

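### Does the primary analysis drop study completers with a missing Week 9-12 outcome from the all-randomized denominator?

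*SAP*

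**What the plan says.** SAP 5.1 fixes the population: "The primary efficacy analysis population will be the Full Analysis Set, defined as all subjects who were randomized". SAP 5 sets the responder-rate convention, under which "subjects who discontinue the study will be included in the denominator but not in the numerator". SAP 7 repeats it as the missing-data rule: "Subjects who discontinue the study will be considered smokers for the remainder of the study regardless of their last smoking status evaluation". Protocol 9.1.1 has the same convention, also worded for discontinuers only.

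SAP 8.1.1.1 describes categorical summaries, with the "denominator being the number of subjects in the analysis set in the particular treatment group with non-missing data". SAP 8.2.3 states that "The 4-week CAR will be summarized by treatment group using descriptive statistics and bar charts", naming no section for that summary, and sends the model to 8.1.1.2. In its multiple-imputation sensitivity analysis, SAP 8.2.3 has a clause for subjects whose outcome is missing without a listed efficacy or safety cause. It extends to those "or who complete the study but have a missing Week 9-12 CAR, will be imputed based on observed subjects in the same treatment group".

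SAP 2.1 defines the endpoint as "complete abstinence from smoking, biochemically verified, during the last 4 weeks of the 12 week dosing period". SAP 6.1 has urine cotinine confirm abstinence at clinic visits. SAP 8.2 makes a positive cotinine test override a self-report of not smoking, and sends missing values to SAP 7.

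**The concern.** Read together, these statements leave one group unplaced. A subject may stay in the study to the end and still lack a Week 9-12 outcome because of a missed visit or test. That subject is not a discontinuer, so the smoker rule in SAP 5 and 7 does not reach them. The SAP knows the group can exist, since it imputes for it, but never says how the primary analysis scores it. SAP 8.1.1.2 gives the logistic model no missing-outcome rule, and standard software drops records with a missing response.

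If the non-missing denominator in 8.1.1.1 applied to the primary endpoint, the reported rate would rest on fewer subjects than the Full Analysis Set. Two programmers could then produce different denominators from the same SAP. If the omissions differed between arms, the odds ratio would move, and a borderline p-value could cross 0.05.

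**Working it through.** **Step 1. Who is affected?** Here 'study completer' means a subject who finished the study, not a member of the SAP 5.2 Completer set, which is defined by dosing days.

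| Subject | Rule in the documents |
|---|---|
| Leaves the study | Smoker, kept in denominator (SAP 5, SAP 7, Protocol 9.1.1) |
| Stops returning for visits | Should be discontinued (Protocol 6.4), hence the same rule |
| Positive cotinine | Smoker (SAP 8.2) |
| Stays in the study, Week 9-12 visit or test missing | Imputed in a sensitivity analysis (SAP 8.2.3); no explicit primary rule |

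Only the last row is open, and two things keep it small. The Nicotine Use Inventory (Protocol Appendix 1) asks about smoking since the last visit, so a later visit can cover self-report across a missed one. What remains is mainly an absent cotinine result, which Protocol 7.3.2 foresees as occasional.

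**Step 2. Does 8.1.1.1 govern the abstinence rate?** The SAP cites 8.1.1.1 in 8.2.1 (baseline characteristics) and in 8.2.5, where users of non-study cessation aids "will be displayed in a table described in" that section. No abstinence section cites it. SAP 5 treats responder-rate denominators separately from generic tables. If an unverified subject is scored as not abstinent, nothing is missing and the two denominators coincide.

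**Step 3. Reproduce the plan's figures.** Inputs from Protocol 9.1: 100 per arm, 9% and 24%, two-sided 0.05.

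- Odds ratio: (24/76)/(9/91) = 3.19; the plan says 3.2.
- Power, pooled chi-square. Mean rate 0.165. Null SE = √(2 × 0.165 × 0.835/100) = 0.0525. Alternative SE = √((0.09 × 0.91 + 0.24 × 0.76)/100) = 0.0514. Then Φ((0.15 − 1.96 × 0.0525)/0.0514) = Φ(0.916) = 82.0%; the plan says approximately 80%, and 80% or greater.
- Enumerating every pair of binomial outcomes gives 83.5%, the reference below.

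**Step 4. Suppose the non-missing rule did apply.** Keep the abstainer counts and remove m non-quitters from a denominator. The odds ratio is [24/(76 − m_v)]/[9/(91 − m_p)], where m_v and m_p are the numbers removed from varenicline and placebo. The counts removed are assumptions.

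| Removed (varenicline/placebo) | Odds ratio | Power | Decision changes |
|---|---|---|---|
| 0/0 | 3.19 | 83.5% | reference |
| 5/5 | (24/71)/(9/86) = 3.23 | 83.5% | 0.0% |
| 10/10 | (24/66)/(9/81) = 3.27 | 83.5% | 0.0% |
| 5/2 | (24/71)/(9/89) = 3.34 | 85.5% | about 2% |
| 2/5 | (24/74)/(9/86) = 3.10 | 80.4% | about 3% |
| 10/3 | (24/66)/(9/88) = 3.56 | 89.0% | about 5% |
| 3/10 | (24/73)/(9/81) = 2.96 | 77.1% | about 6% |

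With 9% in both arms, the type I error is 5.2% under the smoker rule and between 5.0% and 5.2% in the omission scenarios tabulated. Removing 10 from one arm only raises it to 5.7%.

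**Step 5. The other possible reading.** Suppose a self-reported abstainer with no test were counted as abstinent. One such subject per arm gives (25/75)/(10/90) = 3.00, and two per arm give (26/74)/(11/89) = 2.84. The difference in rates stays at 15 points in both cases.

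**The case for a change.** The strongest case for a change is that this is the primary endpoint and the SAP itself names the group. The sensible scoring is an inference. SAP 6.1 says cotinine confirms abstinence, which suggests that an absent test means not abstinent. SAP 8.2 overrides self-report only when a test is positive, which read literally leaves reported abstinence standing when there is no test. A borderline result also shows that the choice can matter. With 19 against 9 abstainers, p = 0.042 on 100 per arm but 0.081 if 10 placebo subjects leave the denominator. With 18 against 9, p = 0.063 becomes 0.030 if 10 varenicline subjects leave.

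Part of this stands: the documents supplied contain no explicit primary-analysis rule for these subjects, and the two cotinine statements do not settle an absent test. The rest is weaker. The borderline examples need 10 missing outcomes in one arm and none in the other, with nothing in the documents to suggest that pattern. They also carry a rule written for descriptive tables into the significance test, although SAP 8.1.1.2 states no such rule. Protocol 9 places detailed methodology in a Statistical Rulebook as well as the SAP. It was not supplied and may hold the rule.

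**Conclusion.** No change to the plan follows. The SAP leaves a detail unwritten that analysts can be expected to fill sensibly. The analysis set is everyone randomized and the endpoint requires biochemical verification, so the natural scoring of an unverified subject is not abstinent, in the denominator. On that reading the denominator texts do not conflict. The planned multiple imputation tests the alternative for this very group.

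A sentence in SAP 7 would record that convention without altering the model, the data or the sample size. It would still leave open what counts as verified when one of the four weekly tests is absent.

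The size cannot be fixed, because the documents give no count of such subjects. Under the illustrative assumptions (100 per arm, 24% and 9%, unadjusted chi-square), equal omission of up to 10 per arm has essentially no effect on power or on the decision. Unequal omission of 5/2 or 2/5 changes the decision in about 2% to 3% of trials, and 10/3 or 3/10 in about 5% to 6%. The conclusion rests on the group being small and not strongly lopsided, which Protocol 6.4 and the design of the Nicotine Use Inventory make likely but do not prove. No error is shown in the primary test or in any figure the plan states.
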